13.1.6 Patients with respiratory failure

Respiratory failure is defined as need for mechanical ventilation, ECMO, noninvasive ventilation, or high-flow nasal cannula oxygen delivery (heated, humidified, oxygen delivered via reinforced nasal cannula at flow rates >20 L/min with fraction of delivered oxygen ≥ 0.5). Other oxygen requirements recorded in the “Other, Specify” field of the eCRF

will be reviewed for any other criteria that may qualify. Any such cases will be identified prior to database lock and unblinding.

The number and percentage of patients with respiratory failure at any time from Baseline to Day 28 will be summarized by treatment. Associated 95% CI for the proportion of respiratory failure will be provided for each treatment group using Clopper-Pearson method. Patients without any post baseline oxygen requirement data recorded will be considered free of respiratory failure.

Changes in O₂ requirements which are considered to be respiratory failure will be flagged in the data listing.

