12.4 Handling of Dropouts or Missing Data

In the analysis of CRP levels if more than 10% of patients in either arm has missing Day 7 CRP values, a supportive analysis will be performed using a mixed model for repeated measures (MMRM). Details of this analysis is provided in [Section 14.1 Inflammatory Biomarkers](#).

Additionally, in the analysis of the PaO₂/FiO₂ ratio if more than 10% of patients in either arm has missing Day 7 values, a supportive analysis will be performed using a mixed model for repeated measures (MMRM). Details of this analysis is provided in [Section 13.1.1 PaO₂/FiO₂ ratio](#).

For any patients with missing results on study day 7, the Day 7 results for coagulopathy, cardiac function damage, the PaO₂/FiO₂ ratio, the WHO ordinal scale and CRP levels will be imputed with the last available assessment, prior to study day 7. Similarly, Day 14 missing observations will be imputed with the last available assessment that occurred after Day 7 and prior to Day 14. Where applicable, Day 28 missing observations will be imputed with the last available assessment that occurred after Day 14. More details are given in the relevant sections of this analysis plan.

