13.1.4 WHO ordinal scale

The WHO ordinal scale is a 10-level ordered categorical scale developed by a special committee at WHO to measure illness severity over time. This endpoint will be collected 4 times during the study: at Baseline and on Days 7, 14, and 28.

The scale will be used to assess patients' clinical status during the study. A 2-point reduction on the score of WHO ordinal scale is considered as clinical improvement.

When completing the WHO Ordinal Scale at Day 14/ EOT, if the patient has received physician orders to be discharged from the hospital, the score should be a 3 or less (*no longer hospitalized*).

Change and percentage change from Baseline to Days 7, 14, and 28 in the scores of WHO ordinal scale as a continuous variable will be summarized by visit and treatment.

A separate summary table will be produced, similar to what is described above, summarizing the results at Day 7 (assessments taking place on study day 7), Day 14 (assessments taking place on study day 14) and Day 28 (assessments taking place on study day 28). For any patients with missing Day 7 results, the Day 7 results will be imputed using the last value reported prior to study day 7. Similarly, Day 14 missing observations will be imputed with the last available assessment that took place after study day 7 and prior to study day 14. Day 28 missing observations will be imputed with the last available assessment that took place after study day 14. A summary table will be produced, summarizing these (imputed and reported) results.

Categorical summaries of patients having a clinical improvement during the study (Baseline to Day 28) will be generated presenting the number and percentage of patients with an improvement at any visit from Baseline to Day 28. Associated 95% CI for the proportion of improvement will be provided for each treatment group using the Clopper-Pearson method.

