The distribution of outcomes on the ordinal scale will also be plotted using stacked bar charts representing the proportion of patients in each category (uninfected, ambulatory mild disease, hospitalized: moderate disease, hospitalized: severe disease and death), by treatment group over time. A second plot will be produced, similar to what is described above, summarizing the results at Day 7 (assessments taking place on study day 7), Day 14 (assessments taking place on study day 14) and Day 28 (assessments taking place on study day 28). For any patients with missing Day 7 results, the Day 7 results will be imputed using the last value reported prior to study day 7. Similarly, Day 14 missing observations will be imputed with the last available assessment that took place after study day 7 and prior to study day 14. Day 28 missing observations will be imputed with the last available assessment that took place after study day 14.

The mean absolute values and mean absolute change from Baseline up to Day 14, using the actual study day for Day14/EOT assessments, will be plotted per treatment group using line graphs.

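### Deaths are not fully handled in two secondary outputs: a death without recorded device need counts as free of respiratory failure, and no rule sets the WHO score to 10 after death.

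*SAP*

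**What the plan says.** **Respiratory failure.** SAP 13.1.6 and Protocol 8.1.6 share one definition: "Respiratory failure is defined as need for mechanical ventilation, ECMO, noninvasive ventilation, or high-flow nasal cannula oxygen delivery". The SAP widens it only through a review of free-text oxygen entries. It then sets a default: "Patients without any post baseline oxygen requirement data recorded will be considered free of respiratory failure". No exception is made for death. The protocol endpoint (Protocol Section 4) is the proportion free of failure to Day 28. The SAP tabulates the complement, within arm: "Associated 95% CI for the proportion of respiratory failure will be provided for each treatment group using Clopper-Pearson method". The analysis set is ITT (SAP Section 12).

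**WHO ordinal scale.** Death is score 10 in the scale table, and the bar charts plot the "proportion of patients in each category (uninfected, ambulatory mild disease, hospitalized: moderate disease, hospitalized: severe disease and death"). On timing, SAP 13.1.4 says: "This endpoint will be collected 4 times during the study: at Baseline and on Days 7, 14, and 28". It also plans a separate summary table and a second plot with carry-forward:
- For patients with "missing Day 7 results, the Day 7 results will be imputed using the last value reported prior to study day 7".
- A missing Day 14 value is "imputed with the last available assessment that took place after study day 7 and prior to study day 14".
- SAP 12.4 adds: "Day 28 missing observations will be imputed with the last available assessment that occurred after Day 14".

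SAP 13.2 repeats its correlation analysis with the same windows. None of these sections says what score a patient has at a visit after death.

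**Death rules elsewhere.** Death is a competing risk in the time-to-event analyses (for example SAP 13.1.2, 13.1.4.1 and 14.1.1). An in-hospital death within 14 days is given 14 days of stay after treatment (SAP 13.1.5). Protocol 10.3 leaves missing-data rules for the efficacy endpoints to the SAP.

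**The concern.** For both outputs, death is the worst result a patient can have. Read literally, the respiratory-failure rule puts some deaths on the favourable side of a secondary endpoint. The WHO windows can replace a death by an earlier living score or remove the patient from the visit. An arm with more deaths could then look better than it should on these two outputs, and an arm with fewer deaths would lose credit.

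The sample size rationale (SAP Section 6) says the estimates will be used to plan future studies, so the values matter even without a formal test. Because the SAP deals with death in neighbouring outputs, this looks like an oversight and not a choice.

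**Working it through.** The plan has no figure to reproduce: it gives no death rate, device-failure rate, WHO change or SD. The only input from the documents is 30 patients per arm (SAP Section 6). All counts and changes below are assumptions, and splits are drug v placebo.

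**1. Respiratory failure, one arm.** A death without device need adds 0 to the failure count but stays in the denominator. Counting k such deaths as not free moves the arm by k/30: 3.3, 6.7 and 10.0 points for k = 1, 2, 3. With 6 device failures, the rate is 6/30 = 20.0% (Clopper-Pearson 95% CI 7.7 to 38.6). Counting 2 such deaths as well gives 8/30 = 26.7% (12.3 to 45.9). The shift is well inside the interval.

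**2. Respiratory failure, between arms.** Take device failures of 5 v 6. The free proportions are 25/30 and 24/30, a difference of +3.3 points whatever the unsupported deaths. The *alive and free* difference depends on them:
- 2 v 0 deaths: 23/30 − 24/30 = −3.3
- 1 v 1: 24/30 − 23/30 = +3.3
- 2 v 2: 23/30 − 22/30 = +3.3
- 0 v 2: 25/30 − 22/30 = +10.0

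**3. WHO carry-forward windows, applied as written (baseline score 5).**

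| Pattern | Day 7 | Day 14 | Day 28 |
|---|---|---|---|
| Death Day 5, nothing entered | 5 | missing | missing |
| Death Day 5, 10 entered once that day | 10 | missing | missing |
| Day 7 score 6, death Day 10, nothing entered | 6 | missing | missing |
| Day 7 score 6, 10 entered once on Day 10 | 6 | 10 | missing |
| Day 7 score 4, discharged Day 10 with 3, death Day 12, nothing entered | 4 | 3 | missing |
| Day 7 score 6, Day 14 score 7, death Day 20, nothing entered | 6 | 7 | missing |

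In the first row the Day 7 value is Baseline, because no WHO score is scheduled between Baseline and Day 7. In the fifth row a dead patient keeps a good score at Day 14, because patients ordered for discharge must score 3 or less (Schedule of Assessments, note 13). A 10 entered after Day 14 does reach Day 28.

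**4. WHO Day 7 size.** An unscored death enters with change 0 instead of 10 − baseline. Per death the arm mean shifts by (10 − baseline)/30: 0.20, 0.17 and 0.13 for baseline 4, 5 and 6.

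**5. WHO Day 28 size.** Assume baseline 5, mean survivor change −3.2 v −3.0, all survivors scored, all deaths by Day 14 and later visits blank. With deaths missing, the difference is −0.20. With a and b deaths scored 10 (change +5):

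difference = (−3.2 + 8.2a/30) − (−3.0 + 8b/30)

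- Equal deaths: 1 v 1 −0.19; 2 v 2 −0.19; 3 v 3 −0.18
- More on drug: 3 v 2 +0.09; 3 v 1 +0.35
- More on placebo: 2 v 3 −0.45; 1 v 3 −0.73

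Each extra death in one arm moves the difference by 8.2/30 or 8/30, about 0.27 points.

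**The case against.** **Respiratory failure and death are separate endpoints.** Someone who dies without respiratory failure has not had respiratory failure. All-cause mortality covers the same 28 days (SAP 13.1.7), and death is in the list compared by Fisher exact test (SAP 11.2). This stands as a reason to keep the protocol endpoint. It does not make a proportion free that includes deaths easy to read.

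**Few deaths should be affected.** Oxygen use is scheduled every treatment day. Patients with a DNR code status, or judged unlikely to survive beyond 2 days, are excluded (Protocol 5.2). This stands. A reader might infer that a stated rule makes every unsupported death free. The documents do not go that far: the explicit default covers only patients with no post-baseline oxygen record. For other deaths the result follows by subtraction, and the word *need* leaves the site some judgement.

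**The WHO scale already has a score for death.** It does, and a death category is plotted, so some entries of 10 are expected. The eCRF is not in the documents, so what sites entered is unknown. If 10 is recorded at every later visit, nothing is lost. A reader might infer that WHO results will be wrong; the documents support only that they can be, if visits are blank or 10 is entered once.

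**The main WHO summary is less exposed.** The windows govern a supplementary table, a second plot and a repeat correlation. In the main summary the Day 14 column is Day 14/EOT (SAP 8.4), so a 10 entered at an earlier end of treatment could appear there. The responder proportion and the time to clinical improvement are not materially affected: an unimproved death is not a responder, and death is a competing risk. All of this stands.

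**The sign changes in step 5 come from a small assumed effect.** Agreed. With an assumed SD of 1 to 3, the 95% half-width is 2.00 × SD × √(2/30), about 0.52 to 1.55, which exceeds 0.27 per extra death. SAP 13.1.4 also names no between-arm WHO model; only the general sentence in SAP 13.1 on continuous measures suggests a comparison.

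**Conclusion.** The point holds as a gap in the rules, and its severity is minor. Deaths without recorded device need count as free of respiratory failure, explicitly when there is no oxygen record and otherwise by subtraction. In the WHO carry-forward outputs, a death can take a living score or go missing when a visit is blank, and a single 10 does not cross the Day 7 or Day 14 boundary.

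The size is 3.3 points per unsupported death in an arm of 30. For WHO it is about 0.17 points per death in the arm mean at Day 7, and about 0.27 in the between-arm difference per extra death at Day 28. The WHO figures rest on the assumed baseline, survivor changes and blank visits.

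A reader might infer a bias in favour of the drug. The documents do not support this: no death rate is given, the direction depends on which arm has more deaths, and equal deaths leave the differences almost unchanged. Nor should the two outputs be read as the only ones affected. Days without oxygen use (SAP 13.1.3), total duration of hospitalization (SAP 13.1.5) and the PaO2/FiO2 and CRP carry-forward also state no death rule.

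**What to change.** Before unblinding:

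1. **SAP 13.1.6.** Keep the protocol endpoint. Add *alive and free of respiratory failure by Day 28*, in which every death by Day 28 counts as not free, whether or not oxygen data exist. Limit the default for missing oxygen data to the protocol endpoint, and show deaths without device need as a separate count beside it. Simply excepting deaths from that default would not be enough: those patients would be left unclassified and treated differently from deaths with some oxygen data.
2. **SAP 12.4, 13.1.4 and 13.2.** Assign WHO score 10 at every scheduled visit on or after the date of death, in observed and imputed outputs, before any carry-forward.
3. **SAP Section 15.** Record the added endpoint; the section now reports no changes.

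The cost is one extra endpoint, a few sentences and minor programming. No new data are needed, because deaths to Day 28 are already collected for the mortality endpoint.

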## The Main Changes Made to Version 2.2 to Generate V 2.3

1. Inclusion criterion #4, “Patients with plasma CRP level  $> 50 \text{ mg/L}$  at screening” has been changed to “Patients with plasma CRP level  $> 50 \text{ mg/L}$  or  $4 \times$  upper limit of normal range at screening”. **Rationale for the change:** In this study, CRP level is measured at local laboratories. Since each laboratory uses different methods with different normal range, it is reasonable to use  $4 \times$  upper limit of normal range as another cut-off in case a local laboratory has high normal range.
2. Exclusion criterion #1, “oxygen delivered via reinforced nasal cannula at flow rates  $> 20 \text{ L/min}$  with fracture of delivered oxygen  $\geq 0.5$ ” has been changed to “oxygen delivered via reinforced nasal cannula at flow rates  $> 20 \text{ L/min}$  with fracture of delivered oxygen  $\geq 0.5$ . However, periodically delivered at flow rates  $> 20 \text{ L/min}$  with fracture of delivered oxygen  $\geq 0.5$  is allowed”. **Rationale for the change:** Some severe COVID patients may need oxygen delivered at flow rates  $> 20 \text{ L/min}$  with fracture of delivered oxygen  $\geq 0.5$  for a short period of time to maintain sufficient oxygen level.
3. Exclusion criterion #5, the following sentence has been added to the end of this criterion: “One dose of dexamethasone at  $> 6 \text{ mg}$  but  $\leq 12 \text{ mg}$  or equivalent is allowed, provided baseline CRP level is measured 24 hours after the dexamethasone dosing at  $> 6 \text{ mg}$  but  $\leq 12 \text{ mg}$ ”. **Rationale for the change:** Change on CRP level induced by one dose of dexamethasone at  $> 6 \text{ mg}$  but  $\leq 12 \text{ mg}$  or equivalent is limited 24 hours after the dosing.
4. Exclusion criterion #13, “suspected or known systemic bacterial or fungal infections” has been changed to “sepsis induced by systemic bacterial or fungal infections”. **Rationale for the change:** Sepsis induced by systemic bacterial or fungal infections will cause hyperinflammation.
5. Prohibited medications, the following sentence has been added after the Janus kinase inhibitor Baricitinib: “Baricitinib at  $\leq 4 \text{ mg/day}$  for less than 7 days prior to screening is allowed. However, this medication should be discontinued after enrollment”. **Rationale for the change:** Based on the information listed in the FDA approved label, baricitinib-induced reduction on CRP level were seen one week after treatment.

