### 5.2. Exclusion Criteria

*Patients should be excluded from this study if any of the following criteria is met at screening visit:*

1. Patient requires endotracheal intubation and mechanical ventilation, oxygen delivered by high-flow nasal cannula (heated, humidified, oxygen delivered via reinforced nasal cannula at flow

rates >20 L/min with fraction of delivered oxygen  $\geq 0.5$ . However, periodically delivered at flow rates >20 L/min with fraction of delivered oxygen  $\geq 0.5$  is allowed), noninvasive positive pressure ventilation, extracorporeal membrane oxygenation (ECMO), or clinical diagnosis of respiratory failure.

2. Patient with shock defined by systolic blood pressure < 90 mm Hg, or diastolic blood pressure < 60 mm Hg or requiring vasopressor.
3. Patient with multi-organ dysfunction or failure.
4. Patient is unlikely to survive beyond 2 days at the discretion of Investigator.
5. Patient has used chronic systemic corticosteroids (for example, >32 mg/day methylprednisolone or equivalent) within 2 weeks prior to screening. However, dexamethasone at a stable dose  $\leq 6$  mg/day or equivalent (such as 31.25 mg of Solu-Medrol) is allowed. One dose of dexamethasone at >6 mg but  $\leq 12$  mg or equivalent is allowed, provided baseline CRP level is measured 24 hours after the dexamethasone dosing at >6 mg but  $\leq 12$  mg.
6. Patient with moderate to severe hepatic impairment by Child-Pugh scoring system.
7. Patients with severe kidney injury requiring dialysis.
8. Patient with any of the following abnormal laboratory values: absolute neutrophil count (ANC) < 2,000 per mm^3, or platelets count <50,000 per mm^3, or alanine aminotransferase (ALT) or aspartate aminotransferase (AST) > 5 x upper limit of normal (ULN) detected within 24 hours at screening (per local lab).
9. Patient has uncontrolled or untreated symptomatic arrhythmias, myocardial infarction or congestive heart failure within the 6 weeks prior to screening.
10. Patient has received immunosuppressant or immunomodulatory drugs within 1 month prior to screening, including anti-cytokine therapies targeting TNF- $\alpha$ , IL-1, IL-6, interferon-beta, or Bruton Tyrosine Kinase (BTK) within 30 days prior to screening. However, remdesivir, convalescent plasma therapy or hydroxychloroquine/chloroquine is allowed in this study.
11. Patient with a code status of do-not-resuscitate (DNR) or cardiopulmonary resuscitate (CPR) Select.

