#### **8.1.6. Free of Respiratory Failure**

Respiratory failure is defined as need for mechanical ventilation, ECMO, noninvasive ventilation, or high-flow nasal cannula oxygen delivery (heated, humidified, oxygen delivered via reinforced nasal cannula at flow rates >20 L/min with fraction of delivered oxygen  $\geq 0.5$ ). Related information will be recorded in the eCRF.

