12 CLINICAL EFFICACY ANALYSES

The clinical efficacy analyses will be based on the ITT set, unless specified otherwise. The mITT set will be primary population for the biomarker analysis with exception of time to 50% reduction of CRP levels for which the ITT set will be primary.

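### Periodic high-flow oxygen is allowed at entry, but the same support counts as respiratory failure, so the endpoint mixes an entry condition with progression

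*SAP*

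**What the plan says.** **Entry.** Exclusion criterion 1 (protocol 5.2, repeated in the synopsis) bars patients who require high-flow nasal oxygen above 20 L/min with FiO2 of 0.5 or more. It then makes an exception: "However, periodically delivered at flow rates >20 L/min with fraction of delivered oxygen" of 0.5 or more is allowed. The list of changes from V2.2 to V2.3 gives the reason: "Some severe COVID patients may need oxygen delivered at flow rates" above 20 L/min "for a short period of time to maintain sufficient oxygen level". No section defines what periodic means. The same criterion also excludes patients whom a clinician has diagnosed with respiratory failure.

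**Endpoint.** Protocol 8.1.6 reads: "Respiratory failure is defined as need for mechanical ventilation, ECMO, noninvasive ventilation, or high-flow nasal cannula oxygen delivery", with the same flow and FiO2 limits. SAP 13.1.6 repeats this: "high-flow nasal cannula oxygen delivery (heated, humidified, oxygen delivered via reinforced nasal cannula at flow rates >20 L/min with fraction of delivered oxygen" of 0.5 or more. It sets the window as follows: "The number and percentage of patients with respiratory failure at any time from Baseline to Day 28 will be summarized by treatment". It adds: "Patients without any post baseline oxygen requirement data recorded will be considered free of respiratory failure". It also says that changes in oxygen requirement judged to be respiratory failure will be flagged in the listing.

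**Analysis set and design.** SAP section 12 states: "The clinical efficacy analyses will be based on the ITT set, unless specified otherwise". SAP section 7 stratifies by age group, dexamethasone use and remdesivir use, not by oxygen support. SAP section 6 plans about 30 patients per group without a power calculation.

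**The concern.** Protocol 8.1 presents efficacy as change from Baseline, so being free of respiratory failure to Day 28 should reflect whether a patient got worse. As defined, the endpoint has no Baseline reference. A patient admitted under the exception meets, or can very easily meet, the failure definition without any deterioration.

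Such patients stay in the ITT denominator and pull the two arms' failure rates together. A chance imbalance between arms in their number also moves the observed difference. The sample size section says that the estimates are meant to help plan later studies, so a diluted rate would be carried forward.

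**Working it through.** The plan gives no event rate, effect size or power for this endpoint, so there is no figure to reproduce. The check has a textual part and an illustration.

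**1. The definitions side by side**

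| Feature | Exclusion 1 | Protocol 8.1.6 / SAP 13.1.6 |
|---|---|---|
| Device | high-flow nasal cannula | the same |
| Thresholds | >20 L/min, FiO2 ≥0.5 | the same |
| Periodic use | allowed | not exempted |
| Minimum duration | not stated | not stated |
| New onset or worsening | not applicable | not required |
| Already met at entry | possible under the exception | no rule |

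The word need in the endpoint does not separate the two, because the reason given for the exception is also that patients may need this oxygen. The SAP's review of free-text oxygen entries looks for further qualifying cases and removes none.

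**2. The two readings of the window**

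- *Baseline use counts.* A window that runs from Baseline reads as inclusive. Every patient on periodic high flow at Baseline is then a failure in either arm.
- *Only post-baseline use counts.* The sentence on missing post-baseline oxygen data and the flagging of changes point this way. A patient who never uses high flow again stays free of failure, and treatment could influence that. One further short spell, of a kind the entry rule tolerates, makes the patient a failure.

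A periodic user with no later oxygen record is a failure on the first reading and free on the second, so two programmers could report different counts.

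**3. Size of the dilution**

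Let q be the share of periodic users, p the failure rate in the other patients, and r the fraction of periodic users counted as failures because of their entry condition. The remaining periodic users are given rate p. Then:

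arm rate = qr + (1 − qr) × p

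difference between arms = (1 − qr) × (p placebo − p active)

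All of q, r and p are assumptions. The worst case is r = 1. With 30% versus 15% in the others:

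| q | Placebo | Active | Difference | Ratio |
|---|---|---|---|---|
| 0% | 30.0% | 15.0% | 15.0 points | 2.00 |
| 5% | 0.05 + 0.95 × 0.30 = 33.5% | 0.05 + 0.95 × 0.15 = 19.25% | 14.25 | 1.74 |
| 10% | 0.10 + 0.90 × 0.30 = 37.0% | 0.10 + 0.90 × 0.15 = 23.5% | 13.5 | 1.57 |
| 20% | 0.20 + 0.80 × 0.30 = 44.0% | 0.20 + 0.80 × 0.15 = 32.0% | 12.0 | 1.38 |

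Varying the assumed rates at q = 20%: 40% versus 20% becomes 52.0% versus 36.0% (ratio 1.44), and 20% versus 10% becomes 36.0% versus 28.0% (ratio 1.29). If only half of the periodic users are counted (r = 0.5), q = 20% gives the q = 10% row.

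For orientation, power at 30 per arm (two-sided 0.05) for 30% versus 15% falls from about 28% at q = 0 to 20% at q = 10% and 16% at q = 20%. It is low throughout, as the plan accepts.

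**4. Chance imbalance**

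Split 60 patients 30/30 at random. With 6 periodic users in total (10%), the arms differ by 4 or more of them with probability 0.19. With 12 (20%), the probability is 0.33. In the worst case, with a rate of 30% in the others and no treatment effect, an imbalance of 4 shifts the difference by (4/30) × (1 − 0.30) = 9.3 points.

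**The case against.** A reader might infer that every patient admitted on periodic high flow fails at entry whatever the treatment, and so can show no benefit. The documents do not support that as a general statement. It holds only if Baseline use counts, and two sentences in SAP 13.1.6 suggest that post-baseline records drive the endpoint. What stands is that the SAP does not settle the matter, and that the post-baseline reading still counts a tolerated spell as failure.

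The consequence is also limited. This is one of eight secondary clinical efficacy endpoints in an unpowered phase 1b trial whose primary outcome is TEAEs. SAP 13.1.6 plans per-arm Clopper-Pearson intervals and no between-arm test. An imbalance of 3 versus 0 failures in 30 gives intervals of about 2% to 27% and 0% to 12%, which overlap; Fisher's exact p is 2 × 4060/34220 = 0.24. A careful reader would not take that for an effect. Change on the WHO scale, where high flow scores 6, is a Baseline-anchored alternative, although it is taken only at Days 7, 14 and 28. These points lower the priority but do not remove the mismatch.

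Finally, counting a first high-flow episode in a patient who entered on nasal prongs is a defensible choice even if the episode is brief, because it moves the patient from WHO score 5 to 6. That objection stands. Exempting all periodic use in every patient would rest on an undefined term and could delete real new events.

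**Conclusion.** The point holds in limited form. The current text admits patients in a state that the endpoint also calls failure, and it has no rule for Baseline status, onset or escalation. On either reading of the window the endpoint mixes an entry condition with progression.

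The size is modest and assumed. In the worst case, with 30% versus 15% in the other patients, a 10% to 20% share of periodic users takes 1.5 to 3 points off a 15-point difference and brings the ratio from 2.0 to between 1.57 and 1.38. It is less if only some of them are counted, and nil if none are enrolled. The definition should be corrected before unblinding. The point does not threaten the primary safety analysis.

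**What to change.** In SAP 13.1.6 and protocol 8.1.6:

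- Count only respiratory failure that starts after the first dose and is new or escalated relative to the patient's Baseline oxygen support. For randomised patients never dosed, the randomisation date can serve, as SAP 13.1.3 already does for oxygen-free days.
- Flag patients on periodic high flow at Baseline from the oxygen eCRFs, which SAP 13.1.3 says hold dates and times. Check that these forms capture intermittent spells, because the documents do not reproduce them.
- For the flagged patients only, fix and document before unblinding an operational rule for what counts as escalation.
- Keep counting new high-flow use in patients who were not on it at Baseline.
- Report two sensitivity analyses: the current definition, with its handling of Baseline use stated, and an analysis excluding Baseline periodic users. That exclusion uses a pre-treatment characteristic, so the randomised comparison is kept.

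If only the SAP is changed, its section 15, which now declares no changes to the protocol analyses, must record it.

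The term respiratory failure also appears in exclusion 1 and in the treatment discontinuation lists (synopsis and protocol 7.1). Those passages should be reconciled with the endpoint definition; which clinical rule is right is not for this review to say.

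The cost is slightly fewer counted events, a blinded classification of the flagged patients, and a little extra programming. No new data collection is expected if the eCRFs record spells as assumed.
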